3.3. Benefit/Risk Assessment

Based on PRCL-02 nonclinical and preliminary clinical data, there are no anticipated risks requiring monitoring beyond those included in the protocol. No clinically significant safety or tolerability concerns have been identified in the previous study (PRCL-SMAD) which included healthy volunteers given up to 86 mg (single dose) and 54 mg (multiple doses, after a loading dose of 300 mg) for 5 days, or in psoriasis patients who received up to 54 mg (multiple doses, after a loading dose of 300 mg) for 28 days.

More information about the known and expected benefits, risks, serious adverse events (SAEs), and reasonably anticipated adverse events (AEs) of PRCL-02 can be found in the Investigator's Brochure (IB; [PRCL-02 2018](#)).

4. Objectives and Endpoints

Table PRCL 2 shows the objectives and endpoints of the study.

Table PRCL 2 Objectives and Endpoints

Objectives	Endpoints
Primary	

 To evaluate the efficacy of PRCL-02 after 12 weeks of once daily oral dosing in patients with moderate to severe chronic plaque psoriasis 	
 A 75% improvement from baseline to Week 12 in the PASI (PASI 75)
Secondary	

 To evaluate the safety and tolerability of PRCL-02 after 12 weeks of once-daily oral dosing in patients with moderate to severe chronic plaque psoriasis 	
 Treatment emergent adverse events

 To characterize the pharmacokinetics of PRCL-02 after multiple once daily oral dosing for 12 weeks, in patients with moderate to severe chronic plaque psoriasis 	
 $AUC_{0-\tau}$, C_{max}, t_{max} at steady state
Exploratory	

 To evaluate clinical response to PRCL-02 over time using PASI (Fredriksson and Pettersson 1978) and sPGA (Chaudhari et al. 2001) 	
 PASI sPGA

 To characterize the PK/PD exposure-response relationships of PRCL-02 	
 The PK/PD relationship of PRCL-02 exposure and PD efficacy and/or safety measures may be explored

Abbreviations: $AUC_{0-\tau}$ = area under the concentration versus time curve from time zero to one dosing interval (24 hrs); C_{max} = maximum observed drug concentration; PASI = Psoriasis Area and Severity Index; PD = pharmacodynamics; PK = pharmacokinetic; sPGA = static physician's global assessment; t_{max} = time to reach maximum observed drug concentration.

5. Study Design

5.1. Overall Design

This is a multicenter, randomized, double-blind, placebo-controlled, parallel design Phase 2a study in patients with moderate to severe chronic plaque psoriasis.

Screening (up to 28 days prior to first dose of study drug) allows for evaluation of inclusion and exclusion criteria. Following Screening, all eligible patients will be randomly assigned (in 1:1:1 ratio) to PRCL-02 Dose 1, PRCL-02 Dose 2, or placebo and will receive study drug for 12 weeks. Following completion of 12-week treatment, all patients will attend Follow-Up Visits at 2, 4, 6 and 8 weeks after the last dose of study drug.

Efficacy and safety assessments will be performed as defined in the Schedule of Activities (Section 2).

Figure PRCL 1 illustrates the study design.

Study governance considerations are described in detail in [Appendix 3](#).

[figure not shown]

Figure PRCL 1

Illustration of study design for Clinical Protocol PRCL-PoC

5.2. Number of Participants

Approximately 27 patients will be enrolled in each of the 3 treatment arms; planned total enrollment is approximately 81 patients.

5.3. End of Study Definition

End of the study is the date for the last patient to complete or discontinue the study.

End of trial is the date of the last visit or last scheduled procedure for the last patient in the study.

5.4. Scientific Rationale for Study Design

The parallel design is a standard design used to assess efficacy in psoriasis. The study is patient- and investigator-blinded to minimize the potential bias.

5.5. Justification for Dose

The planned doses are designed to ensure the evaluation of an exposure range that encompasses the anticipated pharmacologically active exposure range, while being safe and tolerable for this population.

The lower dosing regimen: a 150 mg loading dose followed by a maintenance dose of 25 mg QD for 12 weeks (starting on Day 2) is intended to achieve an efficacious exposure, based on the IC50 for IFN γ in the human whole blood cell assay (40.3 nM or 15.7 ng/mL) (IB Table 4.7).

The higher dosing regimen: a 300 mg loading dose followed by a maintenance dose of 50 mg QD for 12 weeks (starting on Day 2) is anticipated to achieve a maximum efficacious exposure. Both doses are within the dosing range that was safe and well tolerated in the SMAD Part C study, after once daily dosing of up to 54 mg QD (after a loading dose of 300 mg) for 28 days in a psoriasis patient population.

6. Study Population

Prospective approval of protocol deviations to recruitment and enrollment criteria, also known as protocol waivers or exemptions, are not permitted.

6.1. Inclusion Criteria

Patients are eligible to be included in the study only if they meet all of the following criteria. The timeframes included in the below criteria are relative to screening unless otherwise noted.

1. Male and female between 18 to 75 years of age inclusive.
2. Present with moderate to severe psoriasis vulgaris based on the disease diagnostic criteria defined as:
 - Chronic psoriasis vulgaris for at least 6 months prior to randomization.
 - Plaque psoriasis involving at least 10% body surface area (BSA) at both screening and baseline (randomization).
 - Psoriasis Area and Severity Index (PASI) total score of at least 12 at both screening and baseline (randomization).
 - Static Physician's Global Assessment (sPGA) score of ≥ 3 at screening and at randomization (randomization).
3. Are candidates for systemic therapy.
4. Have a body mass index (BMI) within the range of 18 to 40 kg/m^2 , inclusive.
5. Are able and willing to make themselves available for the duration of the study and are willing to follow study restrictions/procedures.
6. Women who are of childbearing potential, who must agree to use 1 highly effective method of contraception, or a combination of 2 effective methods of contraception for the entirety of the study ([Appendix 5](#)).

Women of non-childbearing potential are defined as women who are:

- Infertile due to surgical sterilization (hysterectomy, bilateral oophorectomy, or tubal ligation), congenital anomaly such as mullerian agenesis; or
- Post-menopausal, defined as either:
 - A woman at least 50 years of age with an intact uterus, not on hormone therapy, who had had either:
 - Cessation of menses for at least 1 year; or
 - At least 6 months of spontaneous amenorrhea with a follicle-stimulating hormone $>40 \text{ mIU/mL}$; or
 - A woman 55 years or older not on hormone therapy, who has had at least 6 months of spontaneous amenorrhea; or
- A woman at least 55 years of age with a diagnosis of menopause prior to starting hormone replacement therapy.

6.2. Exclusion Criteria

Patients will be excluded from study enrollment if they meet any of the following criteria. The timeframes included in the below criteria are relative to screening unless otherwise noted.

7. Are Eli Lilly and Company, PRCL Research Inc., or Contract Research Organization employees, investigator or site personnel directly affiliated with this study and the immediate families of either of these. Immediate family is defined as a spouse, parent, child or sibling, whether biological or legally adopted.
8. Are currently enrolled in any other clinical trial involving a study drug or off label use of a drug or device, or any other type of medical research judged not to be scientifically or medically compatible with this study. Patients who participated in the previous PRCL study (SMAD) will be allowed to be included in this study, provide that they meet all inclusion and none of the exclusion criteria.
9. Participated in a clinical study within 30 days (defined as the last dose of study drug), prior to first dosing in this study.
10. Present with pustular, erythrodermic psoriasis, generalized pustular psoriasis or acute guttate psoriasis.
11. Have current serious or unstable illnesses including hepatic, renal, gastroenterologic, respiratory, cardiovascular (including a history of ischemic or structural heart disease, conduction system disease or history of clinically significant arrhythmia), endocrinologic, neurologic, psychiatric, immunologic, hematologic, or dermatologic disease and other conditions that, in the investigator's opinion, could interfere with the analyses of safety and efficacy in this study.
12. Have a history of clinically significant severe drug allergies or severe post-treatment hypersensitivity reactions (including, but not limited to, erythema multiforme major, linear immunoglobulin A (IgA) dermatosis, toxic epidermal necrolysis, or exfoliative dermatitis).
13. Have received inactivated vaccine within 4 weeks prior to dosing in this study, or a live vaccine within 3 months prior to dosing in this study.
14. Present with a history of clinically significant opportunistic infection (e.g., invasive candidiasis or Pneumocystis pneumonia).
15. Had symptomatic herpes zoster within 3 months of randomization, other recent or ongoing infection that, in the opinion of the investigator, poses an unacceptable risk to participate in the study.
16. Present with any of the following laboratory test results:
 - Positive QuantiFERON®-tuberculosis test at screening AND have not been vaccinated for tuberculosis. If result is indeterminate, a single retest will be allowed. If the result of the second test is still indeterminate, the subject will be excluded. Patients who have been vaccinated with BCG at any time in the past do NOT need to undergo testing. Documentation of previous vaccination is required.
 - For women, positive serum pregnancy test.
 - Evidence of HIV infection or are positive for HIV antibodies based on history or point-of-care testing (POCT) at screening

- Positive test for active hepatitis B as defined as:
 - Positive for hepatitis B surface antigen (HBsAg), or
 - Positive for anti-hepatitis B core antibody (HbcAb) and positive for hepatitis B deoxyribonucleic acid (HBV DNA).
- Positive of anti-hepatitis C antibody with confirmed presence of hepatitis C virus by RNA testing, or chronic liver disease with the most recent available aspartate transaminase (AST) or alanine transaminase (ALT) $> 2 \times$ the upper limit of normal (ULN).
- Evidence of clinically significant hepatic or renal impairment, including ALT above $2 \times$ ULN, AST above $1.5 \times$ ULN, total bilirubin (TBL) above $2 \times$ ULN (TBL accepted up to $2 \times$ ULN if direct bilirubin is within normal limits), or estimated glomerular filtration rate (eGFR) < 60 mL/min/1.73m² (based on CKD-EPI calculation method).

17. Clinically significant ECG abnormalities at screening, or clinically significant personal or family history (in a first-degree relative) of heart diseases, including:

- Confirmed corrected QT (QTcF) interval > 450 msec for both men and women.
- Bundle branch blocks and other conduction abnormalities other than:
 - mild first degree atrioventricular block (≤ 205 msec) or
 - QRS duration shorter than 110 msec without bundle branch block morphology.
- Irregular rhythms other than sinus arrhythmia or occasional, rare supraventricular ectopic beats.
- History of unexplained syncope.
- Family history of unexplained sudden death or sudden death due to long QT syndrome.

18. Are receiving any of the following therapies for psoriasis:

- Systemic retinoids within 12 weeks prior to dosing in this study;
- Systemic psoriasis therapy (such as psoralen and ultraviolet A [PUVA] light therapy, cyclosporine, corticosteroids, methotrexate, oral retinoids, mycophenolate mofetil, thioguanine, hydroxyurea, sirolimus, azathioprine) or phototherapy (including ultraviolet B or self-treatment with tanning beds or therapeutic sunbathing) within 4 weeks prior to dosing in this study;
- Topical psoriasis treatment (other than moisturizing emollients) within 2 weeks prior to dosing in this study; or
- Any biologic agent within the following washout periods: 30 days for anti-TNF inhibitors and 90 days for others prior to dosing in this study.

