- ^c Serum pregnancy test at Screening and urine pregnancy test at subsequent visits.
- ^d If the result of the QuantiFERON®-TB Gold test is positive, the patient will be excluded from the study. If result is indeterminate, a single re-test will be allowed. If the result of the second test is positive or still indeterminate, the patient will be excluded from the study. Patients who have been vaccinated with BCG at any time in the past do NOT need to undergo testing. Documentation of previous vaccination is required.
- ^e On days when there is pre-dose PK sampling (at 1 week, 2 weeks, 4 weeks, 8 weeks and 12 weeks after the first dose), the dosing will be at the site after pre-dose sampling (patients will be instructed to not dose at home). The patients will be required to bring to the CRU their study treatment kit with all unused tablets. On all other days, patients should take their medication at approximately the same time in the morning. It is recommended (but not required) that the dose should be taken with food.
- ^f A full physical examination will be conducted at screening and on Week 4. Physical examination must include evaluation of the skin and mucus membranes. A physical examination may be performed at other visits at the investigator's discretion.
- ^g Height at screening visit only.
- ^h Single BP readings and other vital signs (in a seated position) on Day 1 and subsequent visits.
- ⁱ Single 12-lead ECG readings (in supine position, for at least 5 minutes prior to the ECG reading). The screening ECG may be repeated at the investigator's discretion. When scheduled at the same time, the following order of procedures is recommended: ECGs, vital signs, and blood collection (and/or other study procedures).
- ^j Clinical laboratory tests will include hematology, serum chemistry, and urinalysis.
- ^k Pre-dose samples are to be obtained at 1 week, 2 weeks, 4 weeks and 8 weeks weeks after the first dose of study drug. On the last day of dosing (Day 85/Week 12), the following samples are to be collected: pre-dose and 1, 2, 4, 8 hr post last dose. One sample will also be collected on weeks 2, 4, 6 and 8 weeks post last dose. One sample should be taken at the early termination visit, if applicable. Timing of PK sample collection may be adjusted based on clinical needs. Actual sampling dates and times must be accurately recorded.

3. Introduction

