8.1.1. Discontinuation of Inadvertently Enrolled Patients from Study Treatment

If the Sponsor or investigator identifies a patient who did not meet enrollment criteria and was inadvertently enrolled, a discussion must occur between the sponsor designate medical monitor and the investigator to determine if the patient may continue on investigational product. If both agree it is medically appropriate to continue, the investigator must obtain documented approval from the sponsor to allow the inadvertently enrolled patient to continue on investigational product.

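### A BCG-vaccinated patient who is tested and found QuantiFERON-positive is excluded by schedule footnote d but not by exclusion criterion 16

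*Protocol*

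**What the plan says.** Footnote d to Table PRCL 1 (protocol Section 2) attaches to the QuantiFERON row. On a first result it says: "If the result of the QuantiFERON®-TB Gold test is positive, the patient will be excluded from the study". It allows one retest after an indeterminate result and then says: "If the result of the second test is positive or still indeterminate, the patient will be excluded from the study". Neither sentence mentions vaccination.

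Criterion 16 in protocol Section 6.2, first bullet, excludes a patient with "Positive QuantiFERON®-tuberculosis test at screening AND have not been vaccinated for tuberculosis". It also allows one retest after an indeterminate result, but names only one outcome of it: "If the result of the second test is still indeterminate, the subject will be excluded".

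Both places carry the same exemption: "Patients who have been vaccinated with BCG at any time in the past do NOT need to undergo testing". Both require the vaccination to be documented. Neither forbids testing a vaccinated patient. The SAP adds no rule of its own; its schedule (Section 9) refers the reader to the protocol for footnotes.

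**The concern.** An eligibility rule stated in two places should give the same answer in both. Section 6.2 is the formal list, introduced by "Patients will be excluded from study enrollment if they meet any of the following criteria", and it is the natural source for a site's eligibility check. In the case where the two texts differ, that list is the less protective one.

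The stake is consistent eligibility across sites, and patient safety in a narrow case. Section 3.2 describes PRCL-02 as inhibiting T and B cell activation, dosing lasts 12 weeks, and the QuantiFERON test at screening is the only tuberculosis-specific test in the schedule. What a positive result means should not depend on which page a site uses.

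**Working it through.** The documents give no figure to reproduce and no arithmetic applies. The check is to apply each rule, as written, to each combination of vaccination status and test result. I take vaccination for tuberculosis in criterion 16 to mean BCG.

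| Patient and result | Footnote d | Criterion 16 | Agree? |
|---|---|---|---|
| Unvaccinated, positive | Excluded | Excluded | Yes |
| Unvaccinated, indeterminate then positive | Excluded | Excluded (the retest is itself a positive test) | Yes |
| Unvaccinated, indeterminate twice | Excluded | Excluded | Yes |
| Vaccinated with documentation, not tested | Not excluded | Not excluded | Yes |
| Vaccinated, tested, positive | Excluded | Not excluded | **No** |
| Vaccinated, tested, indeterminate then positive | Excluded | Not excluded | **No** |
| Vaccinated, tested, indeterminate twice | Excluded | Excluded as written | Yes |
| Either status, negative, or indeterminate then negative | Not excluded | Not excluded | Yes |

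The last-but-one row rests on reading the indeterminate sentence of criterion 16 as standing alone. If the whole bullet were limited to unvaccinated patients, that row would differ too.

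Three things follow.

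1. The disagreement is confined to a vaccinated patient who is tested and is positive on the first test or the retest. For unvaccinated patients, the missing mention of a positive retest in criterion 16 changes nothing.
2. The case can arise without any error by the site. Testing is not forbidden, and the exemption depends on documentation. A patient without records at screening would be tested, could be positive, and could then produce the record. Criterion 16 turns on whether the patient was vaccinated, not on whether that was documented in time.
3. Read alone and as written, criterion 16 excludes a tested vaccinated patient with two indeterminate results but not one with a positive result. That ordering is hard to see as intended.

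With the wording proposed under the fix, criterion 16 excludes on a positive, on indeterminate then positive, and on indeterminate twice, whatever the vaccination status. Every row then agrees with footnote d.

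**The case against.** The strongest reply is that the two rules differ without contradicting each other. Both state grounds for exclusion. Section 6.2 excludes anyone who meets any listed criterion; it does not say that nothing else excludes, and criterion 16 does not declare a vaccinated positive patient eligible. A site that follows the whole protocol therefore has one answer, which is to exclude. This stands, and it limits the point to a site that works from the list alone.

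It also disposes of a stronger inference from Section 8.1.1, which opens: "If the Sponsor or investigator identifies a patient who did not meet enrollment criteria and was inadvertently enrolled, a discussion must occur". A reader might conclude that, once such a patient was enrolled, nobody could tell whether that procedure applied. The documents do not support going that far: footnote d plainly excludes the patient, and the sponsor as well as the investigator may raise the case.

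Footnote d could instead be read as covering only patients who must be tested, which would remove the conflict. The footnote does not say so.

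The capitalised conjunction in criterion 16 may be deliberate, since it fits the testing exemption. Nothing in the documents shows which text the sponsor intended, so the choice needs the sponsor's confirmation.

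The safety gain from alignment is also narrow. Untested BCG-vaccinated patients will still enrol, so after the fix a vaccinated patient tested and found positive is excluded while a comparable untested one is not. That is a consequence of the exemption, which is a separate choice that this point does not challenge.

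Finally, criterion 15 lets the investigator exclude for "other recent or ongoing infection that, in the opinion of the investigator, poses an unacceptable risk to participate in the study". This is a partial safeguard. It rests on judgement and does not settle what a positive QuantiFERON result means.

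**Conclusion.** The inconsistency is real and should be corrected, but it is narrow. It concerns only BCG-vaccinated patients who are tested and positive, and it does harm only where a site applies Section 6.2 without footnote d. Few patients are likely to be affected; the documents give neither the proportion vaccinated, nor how often exempt patients are tested, nor the positivity rate, so no frequency can be derived.

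A reader might infer that the screening rule fails generally or that the trial's results are at risk. Neither follows. The rules agree for every unvaccinated patient and for every exempt patient who is not tested. Tuberculosis status does not enter the sample-size calculation, the Fisher's exact test or the definitions of the analysis populations, so power and the primary analysis are untouched.

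Confidence is high that the two texts differ. It is lower on whether any patient would be enrolled because of it.

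**What to change.** In criterion 16, first bullet, delete the condition about not having been vaccinated, so that a positive QuantiFERON test at screening excludes by itself. Extend the retest sentence so that a second result that is positive or still indeterminate excludes, as footnote d already provides. Keep the testing exemption for patients with documented BCG vaccination.

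If the sponsor confirms that the vaccination condition was intended, amend footnote d instead: attach the same condition to a positive first test and to a positive retest, and state whether two indeterminate results exclude a vaccinated patient. Either way, the two places should carry one rule.

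The drafting is small: two edits in one bullet, or edits to one footnote. Because an eligibility rule changes, it needs the sponsor's decision and a protocol amendment, which Appendix 3.1.3 requires to be provided to the ethical review boards. No test or visit is added. The first option may produce at most a few more screen failures.

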6.3. Lifestyle Restrictions

Patients will be instructed to avoid alcohol consumption within 24 hours prior to clinical site visit until the last PK blood sample is collected at the respective visits. Patients will also be

instructed to restrict sun exposure throughout the study period. Patients are not to apply any topical hydrating agent/emollient within 24 hours of a clinic visit.

Male patients should avoid donating sperm while participating in this trial and for 4 months after stopping the study treatment.

6.4. Screen Failures

Patients who do not meet the criteria for participation in the study (screen failures) may be rescreened (up to 1 time) and the rescreen should be at the discretion of the investigator after consultation with sponsor designated medical monitor. If the rescreening is performed a week or longer after the screening visit, the patient must sign a new informed consent form and will be assigned a new identification number. Retesting may occur at the discretion of the investigator, and after consultation with the sponsor designated medical monitor, within a week of the screening visit – in such cases a new identification number will not be assigned.

7. Treatments

